### **2.1.4. Rationale for Evaluating Magnesium Citrate in addition to standard therapy**

Current therapeutics for COVID-19 include remdesivir, with the caveat of therapeutic limitations among patients who are intubated or on ECMO. While we propose the use of magnesium citrate and the probiotic Floranex in

non-ICU, COVID-19 subjects, any observed clinical benefit will subvert disease progression. During the design of this protocol, the investigators propose to add Magnesium citrate in addition to current therapy. Current COVID-19 therapeutics will not interfere with the therapeutic benefit of magnesium citrate, and fortunately, the converse is also true. Interpretation of a trial of one agent will be straightforward and may provide the basis for subsequent trials of patients with more severe COVID-19 manifestations.

## **2.2 Study Aims**

### **2.2.1 Study aim**

To compare the efficacy of magnesium citrate plus the probiotic Floranex versus placebo on physiology, immunologic and clinical outcomes among adults hospitalized due to COVID-19 infection.

### **2.2.2 Study hypothesis**

Among adults hospitalized with COVID-19, administration of magnesium citrate plus the probiotic Floranex will improve clinical outcomes by Day 28.

## **2.3 Study Design**

We will conduct an investigator-initiated, single center, blinded, placebo-controlled, randomized clinical trial evaluating magnesium citrate plus the probiotic Floranex for the treatment of adults hospitalized with COVID-19. Patients, treating clinicians, and study personnel will all be blinded to study group assignment.

## **2.4 Outcomes**

### **Primary Outcome**

1. Change in WHO Clinical Progression Scale through Day 7 after completion of therapy

### **Secondary Outcomes**

1. Time to recovery, which is the time to the earlier of final liberation from supplemental oxygen or hospital discharge
2. Hospital mortality to 28-day mortality (assessed on Study Day 29 from randomization)
3. Time to discharge to 28 days after treatment
4. Quantitative change in nasal viral titer
5. Change in systemic CD4+ and CD8+ T cell cytokine expression
6. Change in Oxygen AUC of SaO2/FiO2 through Day 7
7. Quantitative change in systemic immune profile
8. Oxygen-free days through Day 28
9. Ventilator-free days through Day 28
10. Vasopressor-free days through Day 28
11. ICU-free days through Day 28
12. Hospital-free days through Day 28

## **3. STUDY POPULATION AND ENROLLMENT**

### **3.1 Inclusion Criteria**

1. Age  $\geq$ 18 years
2. Currently hospitalized or in an emergency department with anticipated hospitalization.
3. Symptoms of acute respiratory infection, defined as one or more of the following:
  - a. Cough

- b. fever ( $> 37.5^{\circ}\text{C} / 99.5^{\circ}\text{F}$ )
- c. shortness of breath (operationalized as any of the following: subjective shortness of breath reported by patient or surrogate; tachypnea with respiratory rate  $\geq 22$  /minute; hypoxemia, defined as  $\text{SpO}_2 < 92\%$  on room air, new receipt of supplemental oxygen to maintain  $\text{SpO}_2 \geq 92\%$ , or increased supplemental oxygen to maintain  $\text{SpO}_2 \geq 92\%$  for a patient on chronic oxygen therapy).
- d. sore throat

4. Laboratory-confirmed SARS-CoV-2 infection within 10 days prior to randomization

#### **Exclusion Criteria**

- 1. Prisoner
- 2. Pregnancy
- 3. Breast feeding
- 4. Current infectious or noninfectious diarrheal illness
- 5. Unable to randomize within 21 days after onset of acute respiratory infection symptoms
- 6. Unable to randomize after hospital arrival
- 7. Colonic obstruction
- 8. Unresolved hypovolemia
- 9.  $\text{CrCl} < 30\text{ml/min}$
- 10. Hypermagnesemia
- 11. Diagnosis of Long QT syndrome
- 12. Known allergy to magnesium citrate or the probiotic Floranex
- 13. Unresolved electrolyte imbalance such as hypokalemia or hypocalcemia. The patient can be enrolled if electrolytes are corrected and sustained.
- 14. Receipt of  $> 1$  dose of magnesium citrate or any other colonic cleanser in the 7 days prior to enrollment
- 15. Inability to receive enteral medications
- 16. Refusal or inability to be contacted on Day 15 for clinical outcome assessment if discharged prior to Day 15
- 17. Concurrent medical illness that interferes with clinical assessmentPrevious enrollment in this trial
- 18. The treating clinical team does not believe equipoise exists regarding the use of magnesium citrate plus the probiotic Floranex for the treatment of this patient.
- 19. Participating in any other COVID-19 therapeutic trial

#### **3.3 Justification of Exclusion Criteria**

The exclusion criteria are primarily designed for patient safety. In addition to excluding specific vulnerable populations (e.g., prisoners), these criteria are designed to exclude patients for whom receipt of magnesium citrate plus a the probiotic Floranex might increase the risk of serious adverse events.

#### **3.4 Screening**

The site investigator or delegate will screen for hospitalized patients with laboratory confirmed COVID-19 (that is, a positive laboratory test for SARS-CoV-2) or a pending SARS-CoV-2 test. Treating clinicians will also be instructed to contact the site investigator or delegate for patients with a high clinical suspicion of COVID-19.

#### **3.5 Assessment of Eligibility and Exclusion Tracking**

For patients who appear to meet inclusion criteria during screening, an electronic case report form will be completed to determine eligibility and track exclusions. The electronic case report form will be accessed and

stored in the electronic database. At the time of entry into the screening database, the patient will be assigned a screening number.

If a patient appears to meet all eligibility criteria, the site investigator or delegate will approach the treating clinician to ask permission to approach the patient or Legally Authorized Representative (LAR) to confirm eligibility, discuss potential study recruitment, and proceed with informed consent.

For all excluded patients, including refusal by the treating clinician or patient/surrogate, a small number of de-identified variables will be collected including month and year the patient met screening criteria, age, sex, ethnicity, patient location, and reason(s) patient was excluded. For the safety of research personnel and conservation of personal protective equipment, these encounters may occur via telephone or videophone.

### **3.6 Process of Obtaining Informed Consent**

Informed consent will be obtained from the patient or from a surrogate decision maker if the patient lacks decision-making capacity.

In some instances, bringing a paper consent form and pen to the bedside of a patient with known or suspected COVID-19 and then taking these out of the room would violate infection control principles and policies. Given the infectious risk from COVID-19 and potential shortages of personal protective equipment (PPE), there is a moral and practical imperative to minimize face-to-face contact between patients and non-clinical personnel. The current epidemic also presents unique challenges to obtaining consent from participant's legally authorized representative (LAR). To minimize infectious risk, many institutions are not allowing visitors to enter the hospital. Furthermore, the LAR is likely to have been exposed to the patient and may therefore be under self-quarantine at the time of the informed consent discussion.

Therefore, in addition to the traditional approach of an in-person consent discussion and signed paper informed consent document, we will allow use of "no-touch" consent procedures for this trial. Below, we outline three examples of no-touch consent procedures that may be used: (a) a paper-based approach; (b) attestation of informed consent.

#### **3.6.1 Paper-based approach**

1. The informed consent document is delivered to the patient or LAR.
  - a. If the patient or LAR is on-site, the informed consent document may be delivered to the patient or LAR either by research staff or by clinical staff
  - b. If the LAR is off-site, the informed consent document may be emailed, faxed, or otherwise electronically transferred to the LAR (method dictated by institutional policy)
2. Research staff discuss the informed consent document with the patient or LAR either in-person or by telephone or videophone. *This step confirms subject/LAR identity.*
3. If the patient or LAR decides to consent to participate, the patient or LAR signs the paper copy of the informed consent document.
4. A photograph is taken of the signature page of the informed consent document and uploaded into the electronic database (e.g. REDCap).
  - a. If using the patient's device (such as a patient's personal cellular phone), a survey link can be sent to their device to allow direct upload of the image into the electronic database (e.g. REDCap).
  - b. If using a staff device, it must be approved to store PHI by the local institution. In that case, research personnel can take a photograph of the signature page of the informed consent document either directly or through the window or glass door leading into the patient's room. The photograph can then be uploaded into the electronic database. If a staff device is taken into the patient's room to take a photograph it must be able to be disinfected according to local institutional practices.
5. Research staff and witness provide signatures within the electronic database (e.g. REDCap) confirming their participation in the informed consent process.

6. The patient or LAR retains the paper consent document. The image of the signature page may be printed and bundled with a copy of the blank informed consent document for research records.

If a hospital device is provided to facilitate electronic or paper-based consent, that device will be disinfected according to institutional protocols and removed by research staff or clinical staff during the next entry into the patient's room.

This approach complies with relevant regulations and sub-regulator guidance at 45 CFR 46.117, 45 CFR 164.512, 21 CFR 11 Subpart C (11.100–11.300), <https://www.hhs.gov/ohrp/regulations-and-policy/guidance/use-electronic-informed-consent-questions-and-answers/index.html>, <https://www.fda.gov/regulatory-information/search-fda-guidance-documents/informed-consent>

The information for the informed consent discussion will be provided in a formal document (or electronic equivalent) that has been approved by the IRB and in a language comprehensible to the potential participant, using an interpreter if necessary. The information presented in the consent form and by the research staff will detail the nature of the trial and what is expected of participants, including any potential risks or benefits of taking part. It will be clearly stated that the participant is free to withdraw from the trial at any time for any reason without prejudice to future care, and with no obligation to give the reason for withdrawal. Where a patient does not speak English, a short-form consent and qualified interpreter will be employed, using similar “no-touch” principles. Use of an interpreter and the interpreter’s identity will be documented on the electronic consent.

### **3.7 Randomization and Blinding**

Participants confirmed to meet all eligibility criteria who have provided informed consent will be randomized 1:1 to magnesium citrate plus a the probiotic Floranex versus placebo. A randomization code will be provided to the site investigator or delegate from a centralized, web-based platform. Randomization will require provision of the screening number and confirmation of patient eligibility.

Randomization will be completed in permuted blocks of varying size and stratified by site. The randomized sequence allocation will be stored on a secure server and will not be available to site study personnel. Site research personnel will have a unique Personal Identification Number (PIN) to access the randomization system. Each subject will receive a computer-generated randomization ID number. The computer-generated randomization ID number will be provided to the pharmacy who will provide a dose pack containing magnesium citrate plus a the probiotic Floranex or placebo. The participant, treating clinicians, study personnel, and outcome assessors will all remain blinded to group assignment until after the database is locked and blinded analysis is completed.

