## 1.0 Protocol Synopsis

### Study Design

Blinded, single-center, placebo-controlled randomized clinical trial

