### **Randomization**

Eligible participants will be randomized 1:1 to magnesium citrate plus the probiotic Floranex versus placebo. Placebo will be carbonated lemon water for magnesium citrate and over-encapsulated microcrystalline pills for Floranex. Randomization will be completed in permuted blocks of variable size.

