## **4.4 Co-Interventions**

This trial will control the use of magnesium citrate plus the probiotic Floranex vs placebo during the intervention period. Enrolled participants will not receive open-label magnesium citrate or the probiotic Floranex during the intervention period. All other treatment decisions will be made by treating clinicians without influence from the protocol. Administration of other antiviral medications (“rescue therapy”) will be allowed. The decision to administer other antiviral medications will be made by treating clinicians and will be recorded in the case report form. The decision to administer immunomodulating medications, including corticosteroids, will be made by treating clinicians and will be recorded in the case report from.

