### **6.1 Baseline Assessments and Procedures: Hospital Presentation to Randomization (Day 1)**

- Inclusion/exclusion criteria screening
- Pregnancy test (if applicable)
- Informed consent
- Completion of COVID Ordinal Outcomes Scale
- Blood collection for CD4+ and CD8+ T cell cytokine expression
- Nasal Swab testing for SARS-CoV-2
- Completion of the Sequential Organ Failure Assessment (SOFA)
- Evaluation of Acute Respiratory Distress Syndrome (ARDS) by Berlin Criteria
- Baseline Variable Data Collection:
  - Hospital admissions data: date/time of presentation, origin (home, skilled nursing facility, rehabilitation/LTACH, nursing home, outside hospital, outside ICU), location at enrollment (ED, hospital ward, ICU)
  - Demographics (age, sex, race, ethnicity, height, weight)
  - Signs and symptoms/onset date including acute signs/symptoms such as altered mental status, acute hypoxemic respiratory failure, liver function tests, renal function, coagulation studies, SOC chest imaging results
  - Concomitant Medications/Medication History to include:
    - Chronic use of medications such as: corticosteroids, ACE inhibitors, angiotensin receptor blockers, non-steroids or anti-inflammatory drugs
    - Open label antivirals received such as remdesivir
    - Open label immunomodulators
    - Biologic therapy such a convalescent plasma
  - Comorbidities
  - Oxygen/ventilation assessment including S/F ratio, ventilation type, & vasopressor use (if applicable)
  - Vital signs, including highest respiratory rate, lowest systolic blood pressure, and highest heart rate in the 12 hours prior to enrollment (if available)
- Enrollment/Randomization
- First study drug administration

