## 7. STATISTICAL CONSIDERATIONS

### 7.1 Statistical Approach

The primary analysis will be an intention-to-treat comparison of the Day 7 COVID Ordinal Outcome score between patients randomized to magnesium citrate plus a the probiotic Floranex versus placebo. This analysis will be conducted with a proportional odds model using the Day 7 COVID Ordinal Outcome score as the dependent variable, randomized group assignment as the primary independent variable, and the following co-variables: age, sex, baseline COVID Ordinal Outcome score, baseline SOFA score, and duration of acute respiratory infection symptoms prior to randomization. An odds ratio  $>1.0$  indicates more favorable outcomes with magnesium citrate plus the probiotic Floranex on the COVID Ordinal Outcome scale, while an odds ratio  $<1.0$  indicates more favorable outcomes with placebo.

In addition to reporting data for the full trial population we will also report data separately for patients randomized in the ICU (who tend to be more severely ill) and those randomized outside the ICU (who tend to be less severely ill) as well as those with duration of symptoms  $\leq 5$  days prior to randomization and those with  $>5$  days of symptoms prior to randomization.

The anticipated study size is 30 patients. We calculated the sample size under the assumption that we would have an interim analysis after approximately each 10 patients. We calculated the standard error of the log(odds-ratio) statistic with 15 patients per arm based on data from a recently completed trial within the PETAL Network that enrolled patients early in the course of critical illness, the *Vitamin D to Improve Outcomes by Leveraging Early Treatment* (VIOLET) trial. In the VIOLET trial at Day 15, 11.5% of patients had died, 5.8% were on invasive mechanical ventilation, 22.9% remained in the hospital, and the remaining had been discharged from the hospital (Table 1). We used these outcomes in VIOLET to approximate Day 7 outcomes on the COVID Ordinal Outcome scale that we may observe in this trial.

Table 1. Patient status 14 days (“Day 15”) after randomization in the VIOLET trial.

Patient Status	Percentage of patients
Deceased	11.5%
Invasive mechanical ventilation	5.8%
Hospitalized, not on invasive mechanical ventilation	21.9%
Discharged from the hospital	60.8%

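### Randomization is stratified only by site in a one-center trial, so allocation does nothing to limit chance imbalance in baseline oxygen need; one binary oxygen stratum would, at almost no cost

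*Combined protocol and SAP*

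**What the plan says.** The synopsis calls the trial "Blinded, single-center, placebo-controlled randomized clinical trial", and section 2.3 agrees: "investigator-initiated, single center, blinded, placebo-controlled, randomized clinical trial". The synopsis section on randomization names no stratification factor ("Randomization will be completed in permuted blocks of variable size"). Section 3.7 names one: "Randomization will be completed in permuted blocks of varying size and stratified by site". Block sizes are not given. Allocation is 1:1, and section 7.1 sets the size: "The anticipated study size is 30 patients".

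The baseline ordinal score is available in time to be used in allocation. Section 6.1 lists "Completion of COVID Ordinal Outcomes Scale" among the assessments up to randomization, and the Appendix A schedule puts it in the pre-enrollment column. On the Appendix E scale, 4 is hospitalized without oxygen, 5 is oxygen by mask or prongs, and 6 is non-invasive ventilation or high flow.

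The primary analysis in section 7.1 is a proportional odds model with treatment group plus age, sex, baseline ordinal score, baseline SOFA and symptom duration. Section 7.1 also plans looks about every 10 patients, and halts the trial at 20 if no efficacy is seen or the primary endpoint points the wrong way. That rule does not name an estimate. Sections 5.2 and 5.3 list twelve secondary outcomes and four safety outcomes, with no adjustment stated.

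Background treatment is not standardized. Section 4.4 says "The decision to administer immunomodulating medications, including corticosteroids, will be made by treating clinicians". Antivirals are handled in the same way, and use is recorded.

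**The concern.** A stratification factor with a single level leaves plain blocked randomization. That equalizes arm sizes but not arm composition. Eligibility under section 3.1 runs from cough or sore throat alone to hypoxemia on new oxygen, so baseline oxygen need should be strongly prognostic. It is also a step on the primary scale, and section 5.4 itself says that most morbidity relates to hypoxemia.

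With 15 per arm, an uneven split on oxygen need is common. Wherever an analysis is not adjusted for it, the sicker arm looks worse for reasons unrelated to treatment. The 20-patient look matters most, because a halt there is hard to undo and the arms then hold only about 10 patients each.

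**Working it through.** **Inputs from the document.** One center (synopsis, 2.3); 1:1 allocation (synopsis, 3.7); N = 30, 15 per arm (7.1); halting look at 20 (7.1); Day 15 status in Table 1 of 11.5%, 5.8%, 21.9% and 60.8%; efficacy prior SE 0.352 (7.1).

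**Assumptions.** The document gives no share of patients on oxygen at baseline; 50% and 67% are used (30–70% as a wider check). Block sizes are taken as 2/4, 4/6 or 2/4/6.

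**Step 1: the plan's own figure.** N = 30 cannot be reproduced, because section 7.1 gives no target odds ratio, power or SE value. The SE it refers to can be approximated by Var(log OR) = 12 / [N(1 − Σp³)]. With Table 1, Σp³ = 0.237. At N = 30 the SE is √(12 / (30 × 0.763)) = 0.72; at N = 20 it is 0.89.

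**Step 2: chance of an uneven split.** With 15 v 15 and exactly 15 of 30 on oxygen, the hypergeometric probability of a 9–6 split or worse is 47%, and of 10–5 or worse 14%. Letting the number on oxygen vary, 8,000 simulated trials per setting give these chances of an arm difference of 20 points or more:

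| Patients | Site only, 50% on oxygen | Site only, 67% on oxygen | Stratified by oxygen |
|---|---|---|---|
| 30 | 34–35% | 32% | about 0% |
| 20 | 47–49% | 44–46% | 0.4–2.1% |
| 10 | 71–73% | 69–70% | 29–37% |

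Ranges run across the three block sets. An unrestricted 15:15 allocation gives 36% and 33% at 30 patients. Allowing for block sizes and simulation error, the 30-patient figure is about 30–37%. At 30% or 70% on oxygen it is about 29–31%.

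**Step 3: effect on the final primary analysis.** Baseline score is in the model, so imbalance mainly costs precision. In a linear approximation the variance inflation is 1/(1 − r²), where r is the correlation of arm with oxygen need. With half on oxygen and a difference of d patients, r = d/15.

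- d = 3: r = 0.20, variance × 1.04, SE × 1.02
- d = 5: r = 0.33, variance × 1.125, SE × 1.06

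On average r² is 1/(N − 1) = 1/29 = 0.034, which gives about 4% of variance.

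**Step 4: effect where there is no adjustment.** Assume Day 7 discharge of 80% without and 45% with baseline oxygen, and an inert treatment. With 6 v 9 of 15 on oxygen, discharge is (9 × 0.80 + 6 × 0.45)/15 = 0.66 v (6 × 0.80 + 9 × 0.45)/15 = 0.59. The unadjusted odds ratio is (0.66/0.34)/(0.59/0.41) = 1.35. Differences of 4 and 5 patients give 1.49 and 1.65. At 75% v 50% discharge the three values are 1.24, 1.33 and 1.43.

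At the 20-patient look, 6 v 4 of 10 on oxygen, with the active arm the sicker, gives 1/1.35 = 0.74. That is log(1.35)/0.89 = 0.34 SE. For an inert treatment, the chance that an unadjusted estimate falls on the wrong side of 1 rises from 50% to roughly 63%.

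**Step 5: background treatment.** If 80% of patients on oxygen and 20% of the others receive background drugs (assumed), the chance of a 20-point arm difference in their use falls only from about 33–35% to about 23% when allocation is stratified by oxygen.

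**The case against.** The strongest reply is that the primary model already contains the factor. Baseline ordinal score is the oxygen scale, and SOFA is there too. That stands. In the step 4 scenarios, a Mantel-Haenszel odds ratio adjusted for oxygen has a median of 1.00. A reader might take the odds ratios of 1.24–1.65 as bias in the primary result; they apply only to unadjusted comparisons. Even unadjusted, 1.65 is about 0.7 SE. Under the efficacy prior it shrinks to about 1.10, with P(OR > 1) about 0.62 against the 95% trigger. The futility and harm tests use a non-informative prior, so that shrinkage does not help them.

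A reader might also infer that nothing balances the arms. That goes too far: randomization balances in expectation, and the model adjusts for the measured factor. What is missing is any restriction in the allocation itself.

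A third tempting reading is that the document shows steroid and remdesivir use following oxygen need. The Background in section 2.1 ties its treatment recommendation only to mechanical ventilation or ECMO, not to the step between no oxygen and oxygen. The link at that step is plausible, but it is an assumption. Rescue drugs after deterioration (section 4.6) start after randomization, so no allocation scheme can balance them.

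It could be said that the 20-patient rule is meant to use the adjusted odds ratio. It may be, but the text does not say so. A six-term model in 20 patients may also be unstable: in one illustrative fit with assumed covariate effects, about 25% of fits at 20 patients failed or separated. Stratifying does not cure that instability; it makes the result depend less on the model.

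**Conclusion.** The point holds as an inexpensive design improvement. The only stratification factor is empty, and a 20-point imbalance in oxygen need would occur in about 30–37% of trials at 30 patients and 44–49% at 20. With one binary stratum these fall to about 0% and at most about 2%. The figures assume 50–67% on oxygen at baseline and small varying blocks. At 10 patients, stratification helps less.

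For the final primary analysis the benefit is modest: about 4% of variance on average, and less dependence on the model. The benefit is larger for the halting rule at 20 and for the secondary and safety outcomes. Balance in background treatment improves only in part.

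The range of baseline severity also needs settling. The synopsis excludes mechanical ventilation and section 3 does not; section 2.1.4 describes non-ICU patients, while section 7.1 plans reporting for those randomized in the ICU. These passages must be reconciled. The 4-versus-5 cut can be used either way.

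**What to change.** In section 3.7, replace the site factor with baseline COVID Ordinal Outcome score, 4 or below versus 5 or above, and keep permuted blocks of varying size within each of the two strata. Make the synopsis say the same. The primary model needs no new term.

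Add a sentence committing to report steroid, remdesivir and other immunomodulator use by arm, at randomization and through Day 7, as description only. Use after randomization should not enter the model as a plain covariate, because study treatment may affect it.

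The cost is a setting in the web-based randomization system and two or three sentences of protocol, with no extra patients or procedures. The downside is incomplete final blocks in two strata: arm sizes differed by four or more in about 0.2–2.5% of simulated 30-patient trials.
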